9.5.1.3. Electrocardiograms

Results of triplicate ECGs and change from baseline will be summarized with descriptive statistics at each time point. The baseline value is defined as the last non-missing value before the initial administration of study drug. In addition, the number and percentage of subjects with ECG interval values meeting the criteria will be tabulated (eg, QTc \leq 450 ms, >450 to \leq 480 ms, >480 ms to \leq 500 ms, and >500 ms).

A listing of ECG data will be generated.

9.5.1.4. Vital Signs

Descriptive statistics will be provided for the vital signs measurements by scheduled time of evaluation and by treatment group, as well as for the change from baseline. The baseline value is defined as the last non-missing value before the initial administration of study drug. A listing of vital sign data will be generated.

9.5.1.5. Other

Listings of all other safety endpoints (eg, physical examination findings) will be generated.

9.5.2. Pharmacokinetics Analysis

Pharmacokinetic analysis and statistical analysis of PK endpoints will be conducted in accordance with the protocol, SAP, and the Daiichi Sankyo, Inc. Non-Compartmental Analysis Guidelines.

9.5.2.1. Pharmacokinetic Parameters

Pharmacokinetic and statistical analysis will be performed using appropriate software; eg, Phoenix™ WinNonlin® (Version 8.1 or higher, Certara, L.P.) and/or SAS® (Version 9.4 or higher, SAS Institute Inc.).

The following PK parameters will be calculated for dabigatran, quizartinib and AC886, as applicable.

Cmax	Maximum concentration, determined directly from individual concentration-time data
Tmax	Time to reach maximum concentration
t1/2	The observed terminal half-life (for dabigatran only)
AUC0-74 (truncated AUC)	Area under the concentration-time curve from time 0 to 74 hours (for quizartinib and AC886 only)
AUClast	Area under the concentration-time curve from time-zero to the time of the last quantifiable concentration; calculated using the linear trapezoidal rule (for dabigatran only)
AUCinf	Area under the concentration-time curve from time-zero extrapolated to infinity (for dabigatran only)

9.5.2.2. Statistical Analysis of Pharmacokinetic Endpoints

The PK parameters for dabigatran and for quizartinib and AC886 will be determined using non-compartmental modeling and summarized with descriptive statistics.

To assess the effect of quizartinib on the PK of dabigatran, geometric least square mean (Geo LSM) ratios of Cmax, AUClast, and AUCinf from treatments with and without quizartinib, and their 90% confidence intervals (CIs) will be determined. Each comparison will also be made by performing an analysis of covariance (ANCOVA) on the logarithm-transformed Cmax, AUClast, and AUCinf.

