4.1.1. Design Overview

A maximum of 20 eligible healthy subjects will be enrolled. There will be 2 treatment periods: all subjects will receive dabigatran etexilate in Period 1 (Reference Treatment) and quizartinib 2 hours prior to dabigatran etexilate administration in Period 2 (Test Treatment).

Following a Screening Period of up to 21 days where subject eligibility will be confirmed, subjects will be admitted to the clinical research unit (CRU) on the day prior to dosing (Day -1) and remained domiciled in the CRU for the duration of the study. At CRU admission, eligibility will be reconfirmed and baseline safety evaluations, including ECGs recorded in triplicate will be assessed.

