9. STATISTICAL CONSIDERATIONS

9.1. Statistical Hypothesis

This is not a hypothesis testing study.

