9.2. Sample Size Determination

The number of subjects was not based on statistical power considerations; however, a target sample size of 20 was calculated to provide 90% confidence that the estimated ratios (with and without quizartinib) of dabigatran etexilate geometric mean Cmax and AUC values would be within 10% of true population values. The calculation assumed that AUC and Cmax were log-normally distributed with a within subject coefficient of variation (CV%) of <30% for AUC and Cmax.

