9.4. Population for Analysis Sets

9.4.1. Pharmacokinetic Population

The PK analysis will be performed using the PK Population defined as all evaluable subjects who received at least 1 dose of study drug (quizartinib or dabigatran) and has a measurable concentration.

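### Does the ANCOVA named for the primary dabigatran comparison ignore the within-subject pairing?

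*Combined protocol and SAP*

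**What the plan says.** The design is a two-period fixed sequence. Section 4.1.1 states that "all subjects will receive dabigatran etexilate in Period 1 (Reference Treatment) and quizartinib 2 hours prior to dabigatran etexilate administration in Period 2 (Test Treatment"), so each completing subject contributes a pair.

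Section 9.1 says "This is not a hypothesis testing study". The output is therefore an estimate with an interval. Section 9.2 sets the number of subjects by precision: "a target sample size of 20 was calculated to provide 90% confidence that the estimated ratios" of "geometric mean Cmax and AUC values would be within 10% of true population values". The only variance it uses is within-subject, "with a within subject coefficient of variation (CV%) of <30% for AUC and Cmax".

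Section 9.5.2.2 says that the ratios of Cmax, AUClast and AUCinf and their 90% intervals will be determined. It then adds: "Each comparison will also be made by performing an analysis of covariance (ANCOVA) on the logarithm-transformed Cmax, AUClast, and AUCinf". It lists no model terms.

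The PK Population in Section 9.4.1 is "all evaluable subjects who received at least 1 dose of study drug (quizartinib or dabigatran) and has a measurable concentration". It does not require data from both periods.

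Two further statements bear on the point. Section 9.5 describes itself as a summary, with an SAP to be finalised before database lock that will cover populations and missing data. Section 9.5.2 places the PK statistics under the protocol, that SAP and the sponsor's non-compartmental analysis guidelines. The text of the SAP and of the guidelines is not in the supplied document.

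**The concern.** ANCOVA is an odd label here. It is the only model named for the primary endpoints, yet the plan names no covariate and no subject effect. If someone fitted treatment as the only factor to the 40 log values, the pairs would be treated as independent observations, and between-subject variance would inflate the error term. The 90% intervals would be too wide and would cover well above 90%. The benefit of the two-period design would be lost, and the analysis would not match the variance used in Section 9.2.

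Two smaller features add to the unease. The word *also* in Section 9.5.2.2 can be read as announcing a second analysis of the same ratio, without saying which one governs. And the PK Population can admit a subject with one period only, whose value would enter an unpaired model directly. Because the ratio and its interval are the result of this trial, an error here would affect the main conclusion.

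**Working it through.** **1. The plan's own figure.** Section 9.2 gives n = 20, a within-subject CV below 30% and a 10% margin at 90% confidence. On the log scale the within-subject SD is s_w = √ln(1 + CV²). At 30% this is √ln(1.09) = 0.2936. The paired half-width is t(0.95; 19) × s_w × √(2/20) = 1.729 × 0.2936 × 0.3162 = 0.1605, so the interval is the ratio × 0.852 to 1.174. That is wider than 10%. Twenty subjects meet the 10% target in a paired calculation only if the CV is about 18% to 20% (at 20%: × 0.897 to 1.114), which an upper bound of 30% allows. Whether 20 is enough at 30% is a separate question. What matters here is that the calculation is stated in within-subject variance alone, the error variance of a paired analysis.

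**2. What an unpaired model would cost.** The half-width would be t(0.95; 38) × √(2(s_w² + s_b²)/20), with t = 1.686 and s_b² = ln(1 + CV_b²). The documents give no between-subject CV, so CV_b is an assumption. The within-subject CV is held at 30%, where s_w² = 0.0862.

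| Assumed CV_b | s_b² | Half-width (log) | Interval at ratio 1.00 | Width relative to paired |
|---|---|---|---|---|
| 0% | 0 | 0.157 | 0.855–1.169 | 0.98 |
| 30% | 0.0862 | 0.221 | 0.801–1.248 | 1.38 |
| 50% | 0.2231 | 0.297 | 0.743–1.345 | 1.85 |

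For CV_b = 30%: 1.686 × √(2 × 0.1724/20) = 1.686 × 0.1313 = 0.221, and 0.221/0.1605 = 1.38. In 40,000 simulated trials the nominal 90% interval covered about 97.6% at CV_b = 30% and 99.7% at 50%. The paired interval covered about 90% throughout. The arithmetic behind the worry is therefore right, given the unpaired model.

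**3. Is that the model in the plan?** Section 9.5.2.2 states no terms, so a treatment-only model has to be supplied by the reader. It also fits the sentence poorly, because an analysis with treatment alone has no covariate and is not an ANCOVA. Sections 4.1.1 and 9.2 both imply a within-subject comparison. The supposed conflict between 9.2 and 9.5.2.2 appears only if the unpaired model is assumed first.

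**4. How much freedom the gap leaves.** With complete pairs, subject as a fixed effect, subject as a random effect and the paired t method all give the same 90% interval. A covariate measured once per subject takes the same value in both periods, so in such a model it does not alter the within-subject contrast. Period cannot be fitted beside treatment, because in a fixed sequence the two coincide. The point estimate is the same whether or not pairing is used.

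**5. One-period subjects.** With a fixed subject effect, or a paired analysis, they add nothing to the ratio. With a random effect they add a little between-subject information. Both are accepted practice. The definition is limited to evaluable subjects, and Section 9.5 leaves populations and missing data to the SAP.

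**6. The word *also*.** Least squares means come from a fitted linear model, and the ANCOVA is the only one named. The natural reading is that the second sentence describes how the ratios in the first are obtained.

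**The case for a change.** The best case for a change is that the interval is the trial's answer, that a single sentence would settle the model at no operational cost, and that the promise of an SAP is narrower than it looks. Section 9.5 commits the SAP to describing populations and the handling of missing, unused and spurious data, and does not expressly mention model terms. Even a summary might be expected to name a model that suits the design.

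Part of this stands. The terms, any covariate and the force of *also* are not written down, and ANCOVA is a loose label for this design. But these are omissions. They do not show that pairing is ignored or that a wrong interval will be produced. Step 4 also answers the worry about choosing a model after seeing the data: among models that respect the design, complete pairs leave essentially one answer.

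**Conclusion.** The concern does not hold as a defect. The plan leaves its model under-described, and everything else it says about the design and the sample size points to the within-subject comparison that a PK statistician would fit as a matter of course. The widening of about 1.4 to 1.9 times describes a model that the plan does not state. It rests on an assumed between-subject CV of 30% to 50%, on a within-subject CV at the 30% upper bound, and on 20 complete pairs. It would vanish as between-subject variance approached zero. Even in that case the error would be conservative and the ratio itself unchanged. The conclusion assumes that the analysts include a subject effect; the SAP and sponsor guidelines that would confirm this are not in the supplied text, and nothing in the protocol suggests otherwise. No change to the plan follows.

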10. APPENDICES - SUPPORTING DOCUMENTATION AND OPERATIONAL CONSIDERATIONS

10.1. Appendix 1 Regulatory and Ethical Considerations

10.1.1. Regulatory Compliance

The study protocol, the IB, available safety information, recruitment procedures (eg, advertisements), subject information and consent form, any subject written instructions to be given to the subject, information about payments and compensation available to the subjects, and documentation evidencing the investigator's qualifications should be submitted to the independent IRB for ethical review and approval according to local regulations, prior to the study start. The written approval should identify all documents reviewed by name and version.

Changes in the conduct of the study or planned analysis will be documented in a protocol amendment and/or the SAP. Written approval of all protocol amendments and changes to any of the above listed documents must be obtained from the IRB.

The investigator should notify the IRB of deviations from the protocol or SAEs occurring at the study site and other AE reports in accordance with local procedures.

The Sponsor will appoint an investigator. Among other possible duties, the investigator will be responsible for reviewing the Final Clinical Study Report and testifying to the accuracy of the description of the study conduct. Because the investigator should have personal knowledge of the conduct of the study, he or she will normally be chosen from among those investigators who have enrolled and treated at least one subject. However, where an investigator has special knowledge of the field or of the study, the investigator can be chosen prior to enrollment of the first subject. In all cases, the investigator must be chosen prior to locking the data base.

10.1.2. Compliance Statement, Ethics, and Regulatory Compliance

This study will be conducted in compliance with the protocol, the ethical principles that have their origin in the Declaration of Helsinki, the International Council for Harmonization (ICH) consolidated Guideline E6 for Good Clinical Practice (GCP) (CPMP/ICH/135/95), and applicable regulatory requirement(s) including the following:

- US Food and Drug Administration (FDA) GCP Regulations: Code of Federal Regulations (CFR) Title 21, parts 11, 50, 54, 56 and 312 as appropriate and/or;
- Other applicable local regulations.

In addition, the investigator will inform the Sponsor in writing within 24 hours of any urgent safety measures taken by the investigator to protect the study subjects against any immediate hazard, and of any suspected/actual serious GCP non-compliance that the investigator becomes aware of.

10.1.3. Supply of New Information Affecting the Conduct of the Study

When new information becomes available that may adversely affect the safety of subjects or the conduct of the study, the Sponsor will inform all investigators involved in the clinical study.

IRBs, and regulatory authorities of such information, and when needed, will amend the protocol and/or subject information.

The investigator should immediately inform the subject whenever new information becomes available that may be relevant to the subject's consent or may influence the subject's willingness to continue participation in the study. The communication should be documented on medical records, for example, and it should be confirmed whether the subject is willing to remain in the study.

If the subject information is revised, it must be re-approved by the IRB. The investigator should obtain written informed consent to continue participation with the revised written information even if subjects were already informed of the relevant information. The investigator or other responsible personnel who provided explanations and the subject should sign and date the revised ICF.

10.1.4. Informed Consent

In obtaining and documenting informed consent, the investigator should comply with the applicable regulatory requirements, and should adhere to GCP and to the ethical principles that have their origin in the Declaration of Helsinki. The ICF and any revision(s) should be approved by the IRB prior to being provided to potential subjects.

The subject's written informed consent should be documented in the subject's medical records. The ICF should be signed and personally dated by the subject and by the person who conducted the informed consent discussion (not necessarily the investigator). The original signed ICF should be retained in accordance with institutional policy, and a copy of the signed ICF should be provided to the subject. The date and time (if applicable) that informed consent was given must be recorded in the eCRF.

If the subject cannot read, then according to ICH GCP Guideline, Section 4.8.9, an impartial witness should be present during the entire informed consent discussion. This witness should sign the ICF after the subject has consented to their participation. By signing the ICF, the witness attests that the information in the ICF and any other written information was adequately explained to and apparently understood by the subject and that informed consent was freely given by the subject.

A separate special consent for inherited genetic analysis will be obtained from subjects in accordance with health authorities in their particular region/country.

Suggested model text for the ICF for the study and any applicable subparts (PK, PD, etc) is provided in the Sponsor's ICF template for the investigator to prepare the documents to be used at his or her study site. Updates to applicable forms will be communicated via letter from the Sponsor.

For study sites in the United States (US), an additional consent is required for the Health Insurance Portability and Accountability Act (HIPAA).

10.1.5. Subject Confidentiality

The investigators and the Sponsor will preserve the confidentiality of all subjects taking part in the study, in accordance with GCP and local regulations.

The investigator must ensure that the subject's anonymity is maintained. On the eCRFs or other documents submitted to the Sponsor, subjects should be identified by unique subject identification (SID) as designated by the Sponsor. Documents that are not for submission to the Sponsor or the contract research organization (CRO) (eg, signed ICF) should be kept in strict confidence by the investigator.

In compliance with ICH GCP Guidelines, it is required that the investigator and institution permit authorized representatives of the company, of the regulatory agency(s), and the independent IRB direct access to review the subject's original medical records for verification of study-related procedures and data. The investigator is obligated to inform the subject that his/her study-related records will be reviewed by the above named representatives without violating the confidentiality of the subject.

10.1.6. Data Integrity and Quality Assurance

10.1.6.1. Monitoring and Inspections

The Sponsor monitor and regulatory authority inspectors are responsible for contacting and visiting the investigator for the purpose of inspecting the facilities and, upon request, inspecting the various records of the study (eg, eCRFs, source data, and other pertinent documents).

The verification of adherence to the protocol; completeness, accuracy, and consistency of the data; and adherence to ICH GCP and local regulations on the conduct of clinical research will be accomplished through a combination of onsite visits by the monitor and review of study data remotely. The frequency of the monitoring visit will vary based on the activity at each study site. The monitor is responsible for inspecting the eCRFs and ensuring completeness of the study essential documents. The monitor should have access to subject medical records and other study-related records needed to verify the entries on the eCRFs. Detailed information is provided in the monitoring plan.

The monitor will communicate deviations from the protocol, SOPs, GCP and applicable regulations to the investigator and will ensure that appropriate action (s) designed to prevent recurrence of the detected deviations is taken and documented.

The investigator agrees to cooperate with the monitor to ensure that any problems detected in the course of these monitoring visits are addressed to the satisfaction of the sponsor and documented.

In accordance with ICH GCP and the Sponsor's audit plans, this study may be selected for audit by representatives from the Sponsor. Audit of study site facilities (eg, pharmacy, drug storage areas, laboratories) and review of study related records will occur in order to evaluate the study conduct and compliance with the protocol, ICH GCP, and applicable regulatory requirements. The investigator should respond to audit findings.

In the event that a regulatory authority informs the investigator that it intends to conduct an inspection, the Sponsor shall be notified immediately.

10.1.6.2. Data Collection

An eCRF must be completed for each subject. Screen failure information will be collected at the clinical site in a log. All data collected during the study will be recorded in the individual, subject-specific eCRF. Instructions will be provided for the completion of the eCRF and any corrections made will be automatically documented via an "audit trail."

The eCRF should be kept current to enable the study monitor to review the subject's status throughout the course of the study. Upon completion of the subject's eCRF, it will be reviewed and signed off by the investigator via the electronic data capture (EDC) system's electronic signature. This signature will indicate that the investigator inspected or reviewed the data in the subject-specific eCRF, the data queries, and the site notifications and agrees with the eCRF content.

10.1.6.3. Data Management

Each subject will be identified in the database by a unique SID.

To ensure the quality of clinical data across all subjects and study sites, a CRO Clinical and Data Management review will be performed on subject data according to specifications developed by the Sponsor. Data will be vetted both electronically by programmed data rules within the application and manually. Queries generated by rules and raised by reviewers will be generated within the EDC application. During this review, subject data will be checked for consistency, completeness and any apparent discrepancies.

Data received from external sources such as central laboratories will be reconciled to the clinical database.

All AEs will be coded using MedDRA. Serious adverse events in the clinical database will be reconciled with the safety database.

10.1.6.4. Study Documentation and Storage

The investigator will maintain a Signature List of appropriately qualified persons to whom he/she has delegated study duties. All persons authorized to obtain informed consent and make entries and/or corrections on eCRFs will be included on the Signature List.

Investigators will maintain a confidential screening log of all potential study candidates that includes limited information of the subjects, date and outcome of the screening process.

Investigators will be expected to maintain an Enrollment Log of all subjects enrolled in the study indicating their assigned study number.

Investigators will maintain a confidential SID code list. This confidential list of names of all subjects allocated to study numbers on enrolling in the study allows the investigator to reveal the identity of any subject when necessary.

Source documents are original documents, data, and records from which the subject's eCRF data are obtained. These include but are not limited to hospital records, clinical and office charts, laboratory and pharmacy records, diaries, microfiches, X-rays, and correspondence.

Electronic CRF entries may be considered source data if the eCRF is the site of the original recording (ie, there is no other written or electronic record of data). In this study, the study eCRF may be used as source documents.

Records of subjects, source documents, monitoring visit logs, data correction forms, eCRFs, inventory of study drug, regulatory documents (eg, protocol and amendments, IRB correspondence and approvals, approved and signed ICFs, investigator's Agreement, clinical supplies receipts, distribution, and return records), and other Sponsor correspondence pertaining to the study must be kept in appropriate study files at the study site (site specific Trial Master File). Source documents include all recordings and observations or notations of clinical activities and all reports and records necessary for the evaluation and reconstruction of the clinical study. These records will be retained in a secure file for the period required by local laws or regulations or study site policy. Prior to transfer or destruction of these records, the Sponsor must be notified in writing and be given the opportunity to provide further instruction.

